# 12.5 Assessment of Efficacy

All subjects with disease who received at least one dose of study drug and have had their disease reevaluated (or die beforehand), will be included in the efficacy analysis. Per the analysis plan described in section 12.8.2 for all time-to-event outcomes (e.g., survival) identified as secondary endpoints, cumulative incidence and hazard functions will be estimated as conditional survival probabilities until first meeting the defined outcome criteria for efficacy:

- ORR (CR/CRi) and anti-leukemic activity (CR/CRi/PR) after 2 cycles. See Section 9.1.
- Relapse-free and event-free survival
- Overall survival in subjects

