# 5.3 Dose Cohorts

# 5.4 Induction (Cycle 1) and Consolidation (Cycle 2):

Cycle 1: Gemtuzumab Ozogamicin (GO) 3 mg/m^2 IV infusion (up to one 4.5 mg vial) will be given on days +1, +4, and +7 in combination with daily oral administration of Venetoclax during Induction. Based on previous studies, Venetoclax dose will start at 200 mg daily with dose escalation planned over 3 cohorts to identify the recommended phase 2 dose (RP2D). Dose cohort 3 will use the maximum dose of Venetoclax of 600 mg orally daily. Because of evidence of tumor lysis syndrome (TLS) with Venetoclax use in previous CLL studies, we will use a 3-day stepwise ramp up in cycle 1 to the target dose for all cohorts (see Table 1). Patients should expect to be hospitalized throughout Induction/Cycle 1, although medically stable patients may be discharged from the hospital under close supervision at the discretion of the treating physician. Patients do not have to be hospitalized during the first week of consolidation if the treating physician wishes to administer Gemtuzumab (C2D1 and D4) in the outpatient clinic.

Day	Cohort 1 (mg)	Cohort 2 (mg)	Cohort 3 (mg)
-2	50	50	100
-1	100	100	200
0	100	200	400
1–28	200	400	600

Table 1. Venetoclax Ramp-up schedule

Clinical and hematological responses will be assessed after the end of both the induction and consolidation cycles. Bone marrow assessment will occur on day 28 regardless of absolute neutrophil count (ANC) or platelet recovery.

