# 5.6 Transplant-eligible Patients

Patients deemed suitable for transplant may be removed from the study at any point, at the discretion of the treating physician. We suggest a period of 2-3 months between the last dose of Gemtuzumab and the beginning of any HSCT conditioning regimen. In view of the infrequent association of VOD with Gemtuzumab use, we recommend the consideration of alternatives to TBI/TMI-containing protocols, which may increase the risk of VOD, for these patients. Ultimately, the final decision is deferred to the site PI.

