# 6.2.1 Gemtuzumab

# Table 5. Gemtuzumab Delay/Discontinuation

Event	Gemtuzumab Action
Persistent Thrombocytopenia	Discontinue if platelets do not recover to $\ge 100 \times 10^9/L$ after temporary cessation of Venetoclax for four weeks
Persistent neutropenia	Discontinue if ANC does not recover to $\ge 1.0 \times 10^9$ /L after temporary cessation of Venetoclax for four weeks
VOD	Discontinue
Total bilirubin $> 2 \times ULN$ , or AST and/or ALT $> 2.5 \times ULN$	Interrupt until recovery of total bilirubin to ≤2 times ULN and AST and/or ALT to ≤2.5 times ULN.

The scheduled dose will be omitted if there is a delay of 3-6 days between sequential infusions.

Table 6. Gemtuzumab Schedule for Interruptions

Time from missed dose	Action
<3 days	Give missed dose
3-6 days	Skip dose
≥7 days	Off study

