#### Consider discontinuing Venetoclax if toxicities recur despite two dose duration reductions

# 6.3 **Protocol Therapy Discontinuation**

In addition to discontinuation due to therapy-related toxicities as outlined in section **6.1**, a subject will also be discontinued from protocol therapy and then followed up per protocol under the circumstances outlined below. The reason for discontinuation of protocol therapy will be documented on the electronic case report form (eCRF) and should also be discussed with the study sponsor-investigator.

- Documented disease progression
- Unacceptable toxicity
- The treating physician believes a change of therapy would be in the best interest of the subject
- Follow-up bone marrow biopsy demonstrates either significant residual leukemic blasts or significant cytoreduction with a high percentage residual leukemic blasts, but BM study is deemed by the hematopathologist to demonstrate less than a partial response.
- Bone marrow biopsy during maintenance phase shows stable disease but the treating hematologist believes that the Venetoclax is no longer of benefit.
- DLT as defined above or if there is grade 3 neutropenia or thrombocytopenia after holding Venetoclax for four weeks at the end of cycles 1 or 2
- Patient is unable to comply with protocol requirements
- The subject requests to discontinue protocol therapy, whether due to unacceptable toxicity or for other reasons. If a subject decides to prematurely discontinue protocol therapy ("refuses treatment"), the subject should be asked if he or she may still be contacted for further scheduled study assessments. The outcome of that discussion should be documented in both the medical records and in the eCRF.
- A female subject becomes pregnant
- Development of a second malignancy (except for basal cell carcinoma or squamous cell carcinoma of the skin) that requires treatment which would interfere with this study.
- If protocol therapy is interrupted for  $\geq 30$  days.
- Lost to follow up. If a research subject cannot be located to document survival, the subject may be considered "lost to follow-up." All attempts to contact the subject must be documented.

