# 7. STUDY CALENDAR & EVALUATIONS

	Screen	Induction 			Consolidation 			Maintenance Phase 		Follow up 		
	Screen		Cycl	le 1			Cycle 2	,	Cycl	es 3+	Safety F/U	Long-term Follow up
Cycle = 28 days	-28 days 	Ramp up	D1	D15	D28	D1	D15	D28	D1	D15	30 days post Tx	$\begin{array}{c} Q \ 2 \ months \\ (\pm 14 \ days)^4 \end{array}$
REQUIRED ASSESSMENTS												
Informed Consent	X											
Medical history, Prior therapy, trial awareness 	Х											
Physical exam, ECOG Performance status	Х		X	Х		Х	Х	Х	Х	C3	Х	X
Vital signs (temp, HR, BP)	Х		X	Х		Х	Х	Х	Х	C3	Х	X
Height (screening only), weight	Х		X	X		Х	X		Х	C3		X
Con meds, AEs, venetoclax drug diary review 	Х		X	Х		Х	X	Х	Х	C3	Х	X
QLQ-C30, FACT-Fatigue, walk test, chair stands		X 						Х	Q2 			X 
EKG, Echocardiogram	X											
LABORATORY ASSESSMENTS												
Pregnancy test (serum or urine) WOCBP 	-7d											
Hepatitis B/C and HIV screen	Х											
Complete Blood Cell Count with diff (CBC)	Х	X 	X 	X 	Х	X 	X 	Х	X	Х	Х	X
Basic Metabolic Panel (BMP), Uric Acid	Х	X 	X 	X 		X 	X 		Х	Х		X
Albumin, ALT, AST, bili, alk phos, T protein, LDH	Х		X 	X 		X 	X 		Х	Х		X
PT/INR PTT, fibrinogen	Х	X 	X 	X 								
DISEASE ASSESSMENT												
Bone Marrow Aspirate and Biopsy 					X			Х		C3 (if P , C13  , r		
TREATMENT EXPOSURE											•	
Gemtuzumab Ozogamicin (IV)			1,4,7			1,4						
Venetoclax (PO)		-2,-1,0		D1-28	•		D1-28	•	D1	-28		
CORRELATIVE STUDIES (SPECIMEN CO		ION)										
Buccal Swab		X 										
Whole Blood 		X 	D3 		X 			X 	C7 	, C13  , 1	relapse	
Bone Marrow Aspirate  X 					X 			X 		, C13  , 1		
BANKING SAMPLES (SPECIMEN COLLECT												
Whole Blood, Serum and Plasma 		X			X			Х	C7.	, C13, re	lapse	
FOLLOW-UP										,		
Survival status, subsequent therapy												X 

1: Screening assessment needs to be completed within 28 days. **Exception:** Bone marrow aspirate needs to be collected within 14 days prior to initiation of treatment.

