2: See section 5 for treatment plan.

3: A window of  $\pm 3$  days will be applied to all cycle 1 and 2 treatment visits; a  $\pm 7$ -day window will apply for maintenance visits.

4: Subjects without documented disease progression will be followed for disease progression every 2 months ( $\pm 14$  days) for 6 months. Once disease progression is documented, subjects will enter a survival follow up period: every 2 months for 6 months from the time of documented progression.

5: Medical history will capture genetic sequencing results/cytogenetics report, prior substance abuse, organ transplant, history of liver disease and family history of cancer.

6: Drug diary review will be performed on Day 1, prior to dispensing the next cycle of venetoclax.

7: For women of childbearing potential (WOCBP): urine or serum  $\beta$ hCG, within 7 days prior to study registration. If a urine test is positive or cannot be confirmed as negative, a serum pregnancy test will be required.

8: CBC should be performed daily while subjects are in the hospital. Basic metabolic panel (calcium, carbon dioxide, chloride, creatinine, glucose, potassium, sodium, urea nitrogen), coags and uric acid measurements will be performed at least every 8 hours during the ramp up and every 8-12 hours during Cycle 1 Days 1-3 to monitor for tumor lysis syndrome. Subsequently, recommend basic metabolic panel and liver function tests be performed at least three times weekly during the induction phase. Uric acid should be evaluated at further intervals at the discretion of the investigator. Recommend measuring coags weekly during the remainder of the induction phase. During consolidation, recommend measuring these labs daily while patient is in hospital and at least weekly when outpatient, at the discretion of the treating physician. During maintenance, recommend measuring these labs at least once every two weeks when outpatient, at the discretion of the treating physician.

9: Bone Marrow Aspirate and Biopsy and/or evaluation of extramedullary site with immunophenotyping, cytochemistry, and cytogenetics (karyotype  $\pm$  FISH): to be completed at pre-treatment (within 14 days), Day 28  $\pm$  3 days during cycles 1 and 2, and  $\pm$  14 days pre-treatment cycle 7 day 1 (i.e. ~6 mo), pre-treatment cycle 13 day 1 (i.e. ~12 mo), and relapse. Patients in PR at the end of consolidation should have a repeat BM assessment after one month of maintenance.

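### Section 12.5 admits treated patients to the efficacy set only if they were re-evaluated or died, so a living patient with no response assessment can leave the ORR and CR/CRi/PR denominators instead of counting as a non-responder

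*Combined protocol and SAP*

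**What the plan says.** Section 12.5 gives the only stated rule for the efficacy denominator. A subject with disease is included who "received at least one dose of study drug and have had their disease reevaluated (or die beforehand"). It applies this to ORR (CR/CRi) and anti-leukemic activity (CR/CRi/PR) after two cycles, and also to RFS, EFS and OS. It gives no method, timing or minimum treatment for re-evaluation.

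The study calendar in section 7 has one row under its disease-assessment heading, "Bone Marrow Aspirate and Biopsy". Note 9 says this is "to be completed at pre-treatment (within 14 days), Day 28" of cycles 1 and 2, then at about 6 and 12 months and at relapse, with an extra marrow after one month of maintenance for patients in PR. Section 5.4 adds: "Bone marrow assessment will occur on day 28 regardless of absolute neutrophil count (ANC) or platelet recovery". Blood counts sit under laboratory assessments, and note 8 says "CBC should be performed daily while subjects are in the hospital".

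Section 9.1 requires a marrow blast criterion for CR, CRi and PR. Of its three failure categories, resistant disease needs evidence of leukemia in blood or marrow, and the other two are deaths. Section 9.2 defines EFS on all patients entered. Section 12.6.3 will report a flow diagram, the number treated by dose level and the number evaluable for response, but it does not say how treated patients who are not evaluable are scored.

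**The concern.** Entry to the efficacy set depends on something that happens after treatment starts. Deaths before re-evaluation are kept in, but living patients who were never assessed are not mentioned. Patients who stop in the first weeks, some of them for toxicity, can then be missing from the denominator, so poor tolerability could slightly raise the reported response rate.

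Because re-evaluation is undefined, two analysts could also report different ORRs from the same data. One might accept any post-baseline blood count and exclude almost nobody. The other might require an assessment capable of classifying response under 9.1. The expansion cohort in 5.1 is meant to inform efficacy at the recommended dose, so the choice should be made before the data are seen.

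**Working it through.** **Step 1. Can a living patient reach the analysis without an assessment?** The first on-treatment marrow is at Day 28. The plan has several ways to stop before it:
- Section 6.3 ends protocol therapy for "DLT as defined above or if there is grade 3 neutropenia or thrombocytopenia after holding Venetoclax for four weeks", of which a cycle 1 non-hematologic DLT can fall before Day 28. It also lists the physician's decision, the subject's own request, non-compliance and loss to follow-up.
- Table 6 in 6.2.1, "Gemtuzumab Schedule for Interruptions", takes a patient off study at 7 days or more.
- Section 5.6: "Patients deemed suitable for transplant may be removed from the study at any point, at the discretion of the treating physician".

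Note 9 ties no marrow to early discontinuation.

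**Step 2. Does 9.1 classify such a patient?**

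| Patient who stops alive before Day 28, no marrow | Category in 9.1 |
|---|---|
| Leukemia documented in blood | Can be resistant disease, a failure |
| No blood evidence of leukemia | None: not CR, CRi or PR (no marrow), not resistant disease, not a death |

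The second row is the gap.

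**Step 3. Direction and size.** Let N be treated patients, r responders, and m treated, living patients in the second row. The plan states no expected ORR for the combination, no attrition rate and no target, so there is no figure of its own to reproduce.

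- All-treated rate: r/N
- Rate with the m patients excluded: r/(N − m)
- Shift: r/(N − m) − r/N = (r/N) × m/(N − m), which is zero or positive

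Inputs: N = 6 + 6 = 12 at the recommended dose (5.1), and 9 + 6 = 15 to 18 + 6 = 24 overall (synopsis). The response share of one third is an assumption, matching the 33% that 1.2.1 cites for fractionated GO alone. The values of m are assumptions.

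| N | r | m | All treated (exact 95% CI) | After exclusion (exact 95% CI) | Shift, points |
|---|---|---|---|---|---|
| 12 | 4 | 0 | 33.3% (9.9–65.1) | 33.3% (9.9–65.1) | 0 |
| 12 | 4 | 1 | 33.3% (9.9–65.1) | 36.4% (10.9–69.2) | +3.0 |
| 12 | 4 | 2 | 33.3% (9.9–65.1) | 40.0% (12.2–73.8) | +6.7 |
| 15 | 5 | 1 | 33.3% (11.8–61.6) | 35.7% (12.8–64.9) | +2.4 |
| 15 | 5 | 2 | 33.3% (11.8–61.6) | 38.5% (13.9–68.4) | +5.1 |
| 24 | 8 | 1 | 33.3% (15.6–55.3) | 34.8% (16.4–57.3) | +1.4 |
| 24 | 8 | 2 | 33.3% (15.6–55.3) | 36.4% (17.2–59.3) | +3.0 |

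Changing the assumed response share at N = 12, m = 1: 3/12 = 25.0% becomes 3/11 = 27.3% (+2.3), and 8/12 = 66.7% becomes 8/11 = 72.7% (+6.1).

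**Step 4. EFS.** Section 9.2 counts all patients entered and censors event-free patients when last examined, whereas 12.5 would drop the unassessed. If such a patient is censored before the first event, the Kaplan-Meier curve does not change. If last examined later, it does. Assumed example: 12 patients, 6 failures at Day 28, one unassessed patient last examined on Day 40. EFS just after Day 28 is 1 − 6/12 = 50% with that patient and 1 − 6/11 = 45% without.

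**The case against.** The strongest reply is that the affected group is small, and much of that stands.

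- *Follow-up continues after treatment stops.* Section 4 requires follow-up under 7.2 for anyone who has begun treatment, 7.2 follows for progression every 2 months for 6 months, and 7.1 with the calendar adds a 30-day visit with examination and blood count. But 7.2 permits follow-up by phone, so no marrow is guaranteed.
- *Failure can be shown in blood.* A reader might infer that 12.5 excludes every patient without a marrow. The documents do not support that: re-evaluation is undefined, and 9.1 accepts blood evidence for resistant disease. Only patients with neither a marrow nor such evidence are left unclassified.
- *Transplant is an unlikely route.* Section 5.6 suggests 2–3 months between the last GO dose and conditioning, while the last cycle 1 GO dose is Day 7 and the marrow is Day 28. Removal before that marrow is possible on paper, but the point does not rest on it.
- *The endpoints decide nothing.* ORR and CR/CRi/PR carry no target or go/no-go rule. One might go further and say that no test is involved. That is too strong: 12.6.2 plans chi-squared tests between cohorts for categorical variables, sample size permitting.
- *The reader can recover the rate.* The counts promised in 12.6.3 may allow it, but they do not say which rate is the reported ORR.

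A reader might also infer that the mismatch between 12.5 and 9.2 is numerically harmless for EFS. That holds only for a patient censored before the first event.

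**Conclusion.** The concern holds in a limited form. As written, 12.5 can remove treated, living patients who have neither a post-baseline response assessment nor blood evidence of leukemia, and nothing in 9.1, 12.2.2, 12.6.2 or 12.6.3 puts them back as non-responders. Relative to the all-treated rate with such patients counted as non-responders, exclusion raises ORR and CR/CRi/PR whenever there is a responder and never lowers them. This is not a claim about the direction of error from the true response rate.

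The size is modest: about 3 points for one such patient among 12 at a one-third response share, well inside an exact interval of roughly 10% to 65%. Both the number of unassessed patients and the response share are assumptions. If no such patient occurs, there is no effect. Dose finding is not affected. The change is still worth making, because the present rule can drop treated patients and a better denominator needs no new data.

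**What to change.** In 12.5:
1. Make the primary denominator for ORR and CR/CRi/PR all patients with disease who received at least one dose of study drug. This keeps 12.5's own disease and dosing conditions. Do not add an eligibility condition: 12.5 has none, and 12.6.3 foresees ineligible patients who may have received therapy.
2. Count as a non-responder any patient without a documented response meeting 9.1 (CR/CRi for ORR; CR/CRi/PR for anti-leukemic activity), including those with no post-baseline marrow.
3. Define the response-assessed subset as patients with a post-baseline marrow or extramedullary assessment, or with blood evidence of persistent leukemia under 9.1. Report it as a labelled sensitivity analysis.
4. Align the EFS population between 12.5 and 9.2 so that unassessed patients are kept and censored under 9.2's existing rule.

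The cost is a few sentences in 12.5 and matching wording in 9.2, with no new visits or data. The reported ORR may be slightly lower than under the present rule.

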# 12.6 Statistical Analysis Plans

# 12.6.1 Analysis Plans for Primary Objective

DLTs will be presented by dose of Venetoclax when administered with Gemtuzumab Ozogamicin.

# 12.6.2 Analysis Plans for Secondary Objectives

Descriptive characteristics of all adverse effects of GO in combination with Venetoclax (using CTCAE v5 criteria) will be reported; and the efficacy of the combination in achieving ORR (includes CR/CRi) and anti-leukemic activity (includes CR/CRi/PR), as defined by the revised IWG criteria), RFS, EFS, and OS in subjects. The effects of therapy on quality of life, fatigue, and physical function at D0 (trial entry) and the end of every other month for 1 year (see section 8.1) will be reported and analyzed using generalized linear modeling.

All time-to-event outcomes (e.g. survival) will be calculated using Kaplan Meier methods and exploratory log-rank tests will be used to compare treatment effect between groups based on genomic MRD, CD33 DNA polymorphisms, BH3 profiling and anti-apoptosis protein levels in PB MBCs at presentation and after 1 week of Venetoclax.

*Sample size permitting:* Hazard ratios (HR) and 95% CIs will be produced. Time-to-event outcomes with a competing or semi-competing risk (e.g. CIR) will be analyzed using cumulative incidence curves and exploratory comparisons between arms will be made using Grey's test. Rate ratios and 95% CIs will be presented. Chi squared tests will be used to assess the treatment effect between cohorts for all categorical variables and t-tests or Mann Whitney tests will be applied for continuous measures as appropriate.

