# 2.2.2 Secondary Endpoints

- Overall response rate (CR/CRi), as defined by the revised IWG criteria. See Section 9.1.
- Anti-leukemic activity (CR/CRi/PR), as defined by the revised IWG criteria. See Section 9.1.
- Adverse effects will be characterized using the CTCAE v5 criteria.
- Relapse-free survival (RFS), event-free survival (EFS, and overall survival (OS). See Section 9.2
- The European Organization for the Research and Treatment of Cancer 30 item questionnaire (EORTC QLQ-C30), The Functional Assessment of Cancer Therapy Fatigue (FACT-Fatigue) questionnaire, two-minute walk test, and timed chair stands will be performed at trial entry and every other month for 1 year.

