10: Whole blood to be collected pre-treatment, Cycle 1 Day +3 ( $\pm 1$  day), end of induction, end of consolidation, pre-treatment cycle 7 day 1 (i.e.  $\sim 6$  mo), pre-treatment cycle 13 day 1 (i.e.  $\sim 12$  mo), and relapse. See section 8. See Correlative Laboratory Manual (CLM) for collection, labeling, processing, and shipping instructions.

11: Bone marrow aspirate to be collected pre-treatment, end of induction, end of consolidation, pre-treatment cycle 7 day 1 (i.e.  $\sim$ 6 mo), pre-treatment cycle 13 day 1 (i.e.  $\sim$ 12 mo), and relapse. See CLM for collection, labeling, processing, and shipping instructions. Left-over samples will be banked for potential future studies, with patient consent. See section 8.

12: Pre-treatment evaluation includes buccal swab, whole blood collection, QOL (QLQ-C30, FACT-Fatigue), walk test, and chair stands. Pre-treatment bone marrow aspirate will be collected at screening. Aspirate collection for correlative studies is required prior to therapy.

13: QOL (QLQ-C30, FACT-Fatigue), walk test and chair stands to be performed pre-treatment, at the end of consolidation, every other cycle starting with Cycle 4 and throughout long term follow up.

14: Whole Blood, Serum and Plasma for banking to be collected pre-treatment, end of induction, end of consolidation, pre-treatment cycle 7 day 1 (i.e. ~6 mo), pre-treatment cycle 13 day 1 (i.e. ~12 mo), and relapse. See CLM for collection, labeling, processing, and shipping instructions. 15: It is suggested that patients should not receive HSCT conditioning within 2-3 months of last Gemtuzumab dose and that total body irradiation (TBI)/ total marrow irradiation (TMI) as part of a HSCT conditioning regimen be avoided, if possible, per discretion of the site PI.

09JUN2022

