#### 7.2 Long Term Follow-up Evaluations

All subjects will be followed until documented disease progression. Subjects who discontinue treatment for any reason without documented disease progression will be followed for disease progression every 2 months ( $\pm 14$  days) for 6 months.

Once disease progression is documented, subjects will enter a survival follow up period every 2 months ( $\pm 14$  days) for 6 months from the time of documented progression.

Follow up may be accomplished via clinic visit, phone call, or other avenues as appropriate.

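### The quality-of-life and function endpoint runs to 1 year from entry, but scheduled contact ends 6 months after progression or early stopping, so months 8, 10 and 12 are not due for all living patients

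*Combined protocol and SAP*

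**What the plan says.** **The endpoint.** Section 2.2.2 says that the two questionnaires, the walk test and the chair stands "will be performed at trial entry and every other month for 1 year". Sections 8.1.6 and 12.2.2 give the same horizon, and section 12.6.2 plans the analysis of quality of life, fatigue and "physical function at D0 (trial entry) and the end of every other month for 1 year".

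**The collection schedule.** Footnote 13 of the study calendar (section 7) collects these measures before treatment, at the end of consolidation, then "every other cycle starting with Cycle 4 and throughout long term follow up". Off treatment, collection therefore lasts only as long as long-term follow-up does.

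**When follow-up ends.** Section 7.2 sets the survival follow-up after progression at 2-month intervals "for 6 months from the time of documented progression", and footnote 4 agrees. For the other group, section 7.2 says: "Subjects who discontinue treatment for any reason without documented disease progression will be followed for disease progression every 2 months", with a limit of 6 months. The same section opens with "All subjects will be followed until documented disease progression", which that limit contradicts. Contact may be by phone.

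**The analysis.** Sections 12.6.2 and 12.6.3 plan descriptive tables by month, generalized linear models for repeated measures, and generalized estimating equations for dichotomised scores. Neither section says how death or the end of scheduled follow-up is handled.

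**The concern.** The endpoint is timed from entry, while the end of collection is timed from progression or from stopping treatment. A patient who leaves early can be alive at month 12 with no assessment due. These values are absent because the schedule never asks for them, and the trigger is an event likely to go with worse quality of life and function.

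The late by-month means and the late part of any fitted curve would then rest more and more on patients who did well. Section 1.3 gives maintaining or improving quality of life as a hope for the combination, so a flat or rising curve to 1 year could be read as support for it when part of the shape comes from who was still on the schedule.

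**Working it through.** **1. The plan's own schedule.** Every other month for 1 year gives 12 / 2 = 6 post-baseline assessments, at months 2, 4, 6, 8, 10 and 12.

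**2. Patients who stay on treatment.** With 28-day cycles and no delays, day 1 of cycle c falls on study day 28(c − 1) + 1. After the end of consolidation (day 56, month 1.8), cycles 4, 6, 8, 10, 12 and 14 start on days 85, 141, 197, 253, 309 and 365, which is months 2.8, 4.6, 6.5, 8.3, 10.2 and 12.0 at 30.44 days per month. Maintenance has no fixed end (section 5.5), so 1 year is reachable. These dates do not match even months from entry exactly.

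**3. Patients with documented progression at month P.** Last scheduled contact is P + 6, so an assessment at month m is due only if P ≥ m − 6.

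| P (months) | Last contact | Not due |
|---|---|---|
| 1 | 7 | 8, 10, 12 |
| 2 | 8 | 10, 12 |
| 3 | 9 | 10, 12 |
| 4 | 10 | 12 |
| 5 | 11 | 12 |
| 6 or later | 12 or later | none |

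Months 8, 10 and 12 thus need freedom from documented progression to months 2, 4 and 6. The 14-day window is 14 / 30.44 = 0.46 month, which lowers these to about 1.5, 3.5 and 5.5.

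**4. Patients who stop at month T with no progression seen.** Last contact is T + 6, so the same table applies with T in place of P. Section 5.6 lets transplant candidates leave at any point, and section 4 sends everyone who stops treatment to section 7.2. Leaving at month 3 without progression ends contact at month 9, so months 10 and 12 are not due.

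**5. Illustration of scale (assumptions, not a forecast).** Suppose time from entry to progression is exponential and ignore deaths. The share progression-free long enough for month m is 0.5^((m − 6) / median). For a 6-month median: 0.5^(2/6) = 79%, 0.5^(4/6) = 63%, 0.5^(6/6) = 50%.

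| Assumed median | Month 8 | Month 10 | Month 12 |
|---|---|---|---|
| 75 days | 57% | 32% | 18% |
| 4 months | 71% | 50% | 35% |
| 6 months | 79% | 63% | 50% |
| 11 months | 88% | 78% | 69% |

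The 75-day figure is the median time to relapse quoted for venetoclax alone (section 1.2.2). The 6-month figure is the relapse-free survival quoted for an older gemtuzumab schedule (section 1.2.1). Neither describes this trial, and the other two medians are chosen only to show the range. The table shows that the selection is graded, strongest at month 12.

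**The case against.** - **Many patients are covered.** Maintenance is open-ended, and anyone progressing at month 6 or later has contact to month 12. This stands: the endpoint can be delivered for these patients, though not for all.
- **Assessment does not stop at progression.** Footnote 13 carries it into long-term follow-up, so a progressing patient has about 6 / 2 = 3 further assessments. This also stands: the loss is late truncation. But nobody is scheduled more than 6 months after progression, so a model could only extrapolate there.
- **Treatment failure need not be recorded as progression.** Section 6.3 lists progression and a marrow showing less than a partial response as separate reasons for stopping, and section 9.1 has no category named progression. A patient stopping at month 1 or 2 for resistant disease could have contact to between month 1 + 6 = 7 (no progression seen) and month 2 + 6 + 6 = 14 (progression seen at the end of the first window). This makes the share affected uncertain and leaves the cut-off dependent on how the event is recorded.
- **Progression might enter the models.** Section 12.6.3 allows for confounders and clinical characteristics. It neither names nor excludes progression, and a covariate does not supply assessments that were never scheduled.
- **All subjects are to be followed until progression.** Read generously, that opening sentence of section 7.2 would protect patients who stop early without progression. It contradicts the 6-month limit that follows and does nothing for patients who have progressed.
- **The stakes are modest.** This is a single-arm phase Ib study of 15–24 patients. Quality of life is secondary in section 2.1.2 and exploratory in the synopsis, and no decision rule rests on it. This limits the weight of the point but leaves the mismatch in place.

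**Conclusion.** The mismatch is real and follows from the documents by calendar arithmetic alone. Months 8, 10 and 12 are due only for patients free of documented progression to about months 2, 4 and 6, with a parallel cut-off for those who stop early without observed progression. Late summaries therefore describe a group increasingly selected on outcome. A favourable tilt is likely if patients who progress early feel and function worse, which is plausible but not shown in the documents. The primary dose-limiting toxicity endpoint is unaffected.

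Two stronger readings are tempting and are not supported.

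- A reader might infer that the 1-year endpoint cannot be delivered at all, or that every value from month 8 on comes from patients progression-free to month 6. The month-6 condition applies to month 12 only, and patients on maintenance reach 1 year.
- A reader might combine the background figures in section 1.2.1 (33% response, about 6 months' relapse-free survival, 11 months' median survival) and, with exponential times and remission at month 1, set 0.33 × 0.5^(5/6) = 19% still scheduled at month 12 against 0.5^(12/11) = 47% alive. Those inputs come from different studies. The calculation leaves out partial responders and stable disease, who may continue under sections 5.4 and 5.5, and counts every non-responder as progressed. Moving remission to month 2 already gives 0.33 × 0.5^(4/6) = 21%, so 19% is not an upper bound. No figure for the share of living patients missed, or for a bias in questionnaire points, can be fixed from the documents.

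**What to change.** **Preferred.** In section 7.2 and calendar footnotes 4 and 13, schedule the QLQ-C30 and the fatigue questionnaire every 2 months to month 12 from entry for every living, consenting patient, whatever the treatment or progression status. Use phone or mail where there is no visit, and do the walk and chair tests only at visits, since a call cannot supply them. Reconcile the opening sentence of section 7.2 with its 6-month limit.

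**Alternative, with no new data collection.** Restrict the endpoint in sections 2.2.2, 8.1.6, 12.2.2 and 12.6.2 to the period actually scheduled. Report the numbers alive, scheduled and assessed at each visit, and do not describe the result as a 1-year effect of therapy.

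Under either option, state in section 12.6 how death and truncated follow-up are handled.

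**Cost.** The added contact is 12 − (P + 6) = 6 − P months: 5 for progression at month 1, 4 at month 2, 2 at month 4, none from month 6. That is at most about three extra questionnaire rounds (months 8, 10 and 12) per early progressor, and the same for early stoppers with T in place of P. The synopsis gives 18 months of enrolment within a 30-month study, leaving 30 − 18 = 12 months for the last patient entered, so the planned duration need not change. The downsides are some burden on patients who have progressed, and incomplete return.
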